3.5 Study intervention and reference

Before starting the project, PI, co-investigators and research team will visit each participating hospital to discuss about the project's objectives and how we would like to conduct this project during 16 months to the directors of the hospitals. These six hospitals have already participated in Global PPS, led by the PI and research team of this project. Hospital staff will be informed about the study by the PI and a director of hospital (also co-investigator) before starting the project and all prescribers in participating hospitals will be encouraged to participate in the training and surveys.

a. Pre-study phase

Four participating hospitals (MS, XK, LNT and SV) in this study have already participated in Global-PPS since 2017, whilst VTP participated in 2018 and SVK in 2019. Antimicrobial prescription data of all six hospitals are available for the whole of 2019. This is the period when there were no available Lao therapeutic and prophylactic antimicrobial prescribing guidelines. These data will be used in this project to compare the change in proportion of antimicrobial prescriptions and the change in administration route before and after the introduction of the prescribing guidelines (both paper-based and mobile phone app versions). To be able to answer our study question, Lao therapeutic and prophylactic antimicrobial prescribing guidelines were developed to be introduced at month 0 of the project. Details of Lao therapeutic and prophylactic antimicrobial prescribing guidelines are described below.

Lao antimicrobial prescribing guidelines

Lao National antimicrobial prescribing guidelines are based on existing Lao treatment guidelines, current data on infectious disease pathogens and antimicrobial susceptibility patterns in Laos and international antimicrobial prescribing/treatment guidelines (e.g. WHO, CDC, NICE, ISID, Sanford). The guidelines are separated into paediatric and adult guidelines for ease of use. These guidelines include recommendation for therapy, prevention and antibiotic stewardship.

Most recommendations are for empiric treatment. For pathogens and syndromes for which Lao data are available, common causative pathogens and their antimicrobial susceptibilities are provided as a guide. This guideline also refers to some specific Lao treatment guidelines (e.g. Dengue guideline for diagnosis and treatment, Lao PDR or National Guidelines for the Use of Antiretroviral Therapy in Adults and Children) to avoid duplication.

Common and important infectious diseases are arranged by involved organ systems. Each infectious disease section includes causative pathogen (s) of the diseases, choices of antimicrobial regimen (primary and alternative), doses, duration and important notes on allergy or toxicity or to help guide treatment.

b. Reference phase

Study duration will be divided into two parts, reference and intervention phases. At the start (month 0), a point prevalence survey (PPS) on hospital antimicrobial use will be performed (more details on conduct of PPS are given in following section) to collect baseline data before introducing paper-based guidelines. The participating hospitals will receive a report of the PPS findings within one month of the survey (Appendix A4).

After PPS, all medical doctors of each participating hospital will be asked to complete an AMS knowledge survey (Appendix A5) and pre-prescribing guidelines survey (Appendix A9). Then, paper-based prescribing guidelines in both adult and paediatric versions (one adult guideline and one paediatric guideline) will be distributed to all doctors at participating hospitals, followed by guideline introductory session of the guidelines (Appendix A6). This session will not cover how to diagnose infectious diseases or prescribe antimicrobials but how to use these guidelines.

After introduction of the paper-based guidelines, all six hospitals will be formally included in the reference period. PI and research team will not become involved with any antimicrobial prescribing decisions of local prescribers at participating hospitals for individual patients. There will be contact details of the PI in the guidelines in case any prescribers need more clarification on the guidelines. A prescriber feedback survey on the paper-based version will be performed just before each paired hospital enters to the intervention phase (month 4, month 8 and month 12 after introduction of the paper-based prescribing guidelines).

After the first paired hospital is randomly selected to have access to the mobile phone app prescribing guidelines at month 4, the second pair of hospitals will be randomly selected to have access to the mobile phone app at month 8, and the last pair of hospitals will have access to a mobile phone app at month 12 (Figure 2).

The order of activities at the start of the project are listed below (these activities will be applied to all six hospitals, one by one):

1. PPS on hospital antimicrobial use for all 6 hospitals (Appendix A1, A2 and A3)
2. AMS knowledge survey (Appendix A5)
3. Pre-prescribing guidelines survey (Appendix A9)
4. Access to paper prescribing guidelines for all 6 hospitals
5. Introductory session to paper prescribing guidelines (Appendix A6)
6. PPS reports (Appendix A4)

Activities in the reference phase after the start of the project (month 0) until the last paired hospital is assigned to the intervention (month 12) are listed below:

1. PPS on hospital antimicrobial use (Appendix A1, A2 and A3)
2. PPS reports (Appendix A4)

c. Intervention phase

c.1 Antimicrobial Prescribing guidelines mobile phone application (MicroGuide)

Both paediatric and adult antimicrobial prescribing guidelines will be transferred to [MicroGuide](#); which is a medical guideline application. MicroGuide was launched in 2013 and has been adopted by 114 medical organizations, with more than 100,000 users in 173 countries. MicroGuide is an offline application, free-of-charge for the individual users. The app can monitor the number of users and which guidelines are being accessed.

The app will be installed to the personal smart phones of local physicians by the PI. The project will not provide a smart phone to any physician without one (approximately <10% of physicians in provincial hospitals– unpublished data). The contents of the mobile app guidelines will be the same as the paper version but using hyperlinks to information, rather than displaying it as in paper guidelines. Both mobile app and paper guidelines will be available in Lao and English languages.

c.2 Antimicrobial stewardship (AMS) training

The aim of AMS training is to increase knowledge and awareness of rational antimicrobial prescriptions of Lao prescribers. AMS training sessions will be given to all prescribers in participating hospitals when they firstly enter to the intervention phase. This session will be given alongside an introduction of mobile phone app prescribing guideline. The training details will be based on the existing information in the paper-based therapeutic and prophylactic antimicrobial prescribing guidelines. The main part of the training will focus on good practices of antimicrobial prescription. Prescribers can also access information on AMS in both paper-based and mobile phone app prescribing guidelines by themselves. Providing training after introducing treatment guidelines is not routine practice in many hospitals in Laos. The combination of the AMS training and easy access to prescribing guidelines could be a new strategy to improve rational use of antimicrobial of Lao prescribers. For more details on how the training will be conducted see Appendix A12. *Antimicrobial Stewardship Training.*

c.3 Intervention delivery

The intervention period will start at month 4 after introducing the paper-based prescribing guidelines. This intervention will be introduced in one pair of hospitals at a time. The process will be repeated every 4 months until all six hospitals have access to the intervention. The order of the activities during intervention phase of each step (paired hospitals) are listed below:

1. PPS on hospital antimicrobial use (Appendix A1, A2 and A3)
2. AMS knowledge survey (Appendix A5)
3. Prescriber feedback survey on paper-based prescribing guidelines (Appendix A10)
4. Access to MicroGuide mobile phone app prescribing guidelines
5. Introductory session on MicroGuide mobile phone app prescribing guidelines (Appendix A7)
6. AMS training session (Appendix A12)
7. PPS reports (Appendix A4)

Note:

- a. A survey on the mobile phone app prescribing guidelines (Appendix A11) will be performed at the end of the project only when all participating hospitals have access to the mobile phone app prescribing guidelines (month 16).
- b. During the intervention period, prescribers in participating hospitals still have access to paper-based prescribing guidelines distributed at the start of the study. Mobile phone prescribing guidelines surveys (Appendix A11) will be used as a tool to access the use of the mobile phone app prescribing guidelines and the paper prescribing guidelines at the end of the study

Figure 2: Study procedures of SW-CRT on Evaluation of Lao-language antimicrobial use guidelines mobile app

	Study phase				
	Pre-study phase				
Hospital 6	PPS+Report	PPS+Report+Paper-based	PPS+Report+Paper-based	PPS+Report+Paper-based	PPS+Report+App+AMS
Hospital 5	PPS+Report	PPS+Report+Paper-based	PPS+Report+Paper-based	PPS+Report+Paper-based	PPS+Report+App+AMS
Hospital 4	PPS+Report	PPS+Report+Paper-based	PPS+Report+Paper-based	PPS+Report+App+AMS	PPS+Report+App+AMS
Hospital 3	PPS+Report	PPS+Report+Paper-based	PPS+Report+Paper-based	PPS+Report+App+AMS	PPS+Report+App+AMS
Hospital 2	PPS+Report	PPS+Report+Paper-based	PPS+Report+App+AMS	PPS+Report+App+AMS	PPS+Report+App+AMS
Hospital 1	PPS+Report	PPS+Report+Paper-based	PPS+Report+App+AMS	PPS+Report+App+AMS	PPS+Report+App+AMS
	Month 0	Month 4	Month 8	Month 12	Month 16
	Activity at month 0	Activity at month 4	Activity at month 8	Activity at month 12	Activity at month 16
	AMS survey for all sites	AMS survey*	AMS survey*	AMS survey*	AMS survey for all sites
	Pre-prescribing survey	AMS training*	AMS training*	AMS training*	Prescriber feedback survey on the App guideline**
	Introduce paper-based guideline	Introduce App guideline*	Introduce App guideline*	Introduce App guideline*	
		Prescriber feedback survey on paper-based guideline*	Prescriber feedback survey on paper-based guideline*	Prescriber feedback survey on paper-based guideline*	
			Prescriber feedback survey on the App guideline**	Prescriber feedback survey on the App guideline**	

* This activity will only be performed in a new selected paired hospital

** This activity will only be performed 4 months after introducing App guideline in each paired hospital

c.4 Contamination prevention

Although the clusters are geographically quite remote from each other, travel and communications between doctors in Laos is quite frequent. There is a possibility of contamination of the app to the reference group (however this is judged to be unlikely). The research team will record this if it occurs. Examples of how this could happen are:

- Doctors from the intervention group move to the reference group for any possible reason (training or changing workplace)
- Doctors from the intervention group give their smart phones to other doctors in the reference group (unlikely)
- Doctors from the intervention group lose their smart phones that are subsequently found and used by doctors in a reference group (unlikely)

To avoid or reduce the problem of contamination, at the start of the intervention phase, all participating hospitals will be requested to avoid sharing the mobile app prescribing guidelines to anybody outside their hospitals while they are still under evaluation. The app guidelines will be installed by the PI. This prescribing guidelines App will not be publicly available on the internet to download by users without the approval from the PI. Transferring the App from one phone to other device will be prevented by informatic code provided by the MicroGuide team. The functional system, security and app maintenance will be controlled by the MicroGuide team and PI of the project.

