The Lao Food and Drug Department (FDD) is responsible for drug registration, licensing of pharmacies/drug companies/drug industries, and overseeing their distribution, import, drug quality control, domestic manufacture and also monitoring the supply chain. In 2016, 218 antibiotic active pharmaceutical ingredients (APIs) and combination APIs were registered by the Lao FDD; of these 38 (17%) were produced in Laos. The main sources of packaged antibiotics are from neighbouring countries such as Thailand and China (<http://www.fdd.gov.la/showContent.php?contID=48>).

In 2006, Keohavong *et al.* described that nearly half (47%) of Lao outpatients within 30 health

facilities investigated throughout the entire country were prescribed antibiotics for mild diseases such as simple diarrhoea or common colds (19). Few data on hospital antimicrobial use exist in Laos; at one northern provincial hospital, 51% of 1,095 patients (2008-2010) received antibiotics but only 7% of these received appropriate antibiotics (20). Nearly 70% of Lao doctors prescribed antibiotics at least once daily and stated that they had not received much information on appropriate antibiotic use during their careers. The doctors stated that they mainly prescribed antibiotics according to the National Standard Treatment Guidelines, advice from their peers, more experienced colleagues, pharmaceutical companies or the Internet. Doctors indicated a preference for local antibiotic guidelines written in Lao language to international ones in other languages (21).

The first hospital antibiotic use survey in Laos was conducted in 2017 using the Global Point Prevalence Survey methodology (LOMWRU, unpublished data). In 2018, five general hospitals across Laos participated in this survey, including two from the north, two from the centre and one from the south of Laos. Of 1,981 in-patient hospitals chart screened, 72% documented an antimicrobial (s) prescription, 43% patients received more than one antimicrobial, 98% were prescribed empirically and nearly half of them received antimicrobials for prophylaxis (LOMWRU, unpublished data). These hospital antimicrobial prescribing rates were much higher than rates (47%) reported in 2006 by Keohavong *et al.* (2006) (19).

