Although the severity of the AMR situation in Laos remains lower than elsewhere in Asia, misuse of antimicrobials is a major driver of resistance. This is a therefore an important opportunity for implementation of a simple technology, which may help reduce further worsening of the AMR situation. Antimicrobial prescribing apps are a promising tool to improve prescribing. However, there has been no evidence from trials to support whether the antimicrobial prescribing guidelines in the format of a mobile phone application are superior to conventional means (i.e. paper-based) in low- and middle-income countries (LMIC). This trial could have a significant impact in Laos and in other LMICs, and inform policy globally, by improving prescribing and hence reducing AMR.

II. Study objectives and hypothesis

Study objectives

Primary objective

To compare the proportion of antimicrobial prescriptions adherent with prescribing guidelines delivered by mobile phone application (app) versus paper-based prescribing guidelines in both in- and outpatients in six general hospitals in Laos

Secondary objectives

1. To compare the change in antimicrobial defined daily doses (DDDs) after introduction of paper-based versus mobile phone app prescribing guidelines plus antimicrobial stewardship (AMS) training in both in- and out patients

2. To compare the change in proportion of patients receiving intravenous antimicrobials route between paper-based and mobile phone app prescribing guidelines + AMS training in both in- and out patients
3. To compare the AMS knowledge level of the prescribers before and after prescribing guidelines delivered by mobile phone app and AMS training
4. To compare the prescriber satisfaction with/acceptability of paper-based prescribing guidelines versus mobile phone app prescribing guidelines
5. To compare antimicrobial costs before and after prescribing guidelines delivered by mobile phone app and AMS training in both in- and outpatient departments
6. To compare the proportion of patients admitted to hospital receiving an antimicrobial prescription before and after introduction of the paper-based prescribing guidelines; and the mobile phone app prescribing guidelines + AMS training

III. Methods

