3.6 Endpoints

Primary endpoint

The proportion of antimicrobial prescriptions adherent with prescribing guidelines delivered by mobile phone app versus paper-based prescribing guidelines at month 16 (12 months' exposure in each group)

Secondary endpoints

1. Total antimicrobial defined daily doses (DDDs) prescribed in mobile phone app versus paper-based groups of 12 months' exposure in each group

2. Proportion of patients prescribed antimicrobials by the intravenous route in mobile phone app versus paper-based groups of 12 months' exposure in each group
3. AMS knowledge level of prescribers prescribed in mobile phone app versus paper-based groups of 12 months' exposure in each group
4. Prescriber satisfaction/acceptability of the prescribing guidelines in mobile phone app versus paper-based groups of 4 months' exposure in each group
5. Total costs of antimicrobial prescribed in mobile phone app versus paper-based groups of 12 months' exposure in each group
6. Proportion of patients admitted to hospital receiving an antimicrobial prescription before and after introduction of the paper-based prescribing guidelines; and the mobile phone app prescribing guidelines + AMS training of 12 months' exposure in each group

Definitions of adherence to the guidelines

1. Full adherence with the guidelines = using correct antimicrobial agent (s) and correct dose based on the provided antimicrobial prescribing guidelines
2. Partial adherence with the guidelines = using correct antimicrobial agent (s) with incorrect dose based on provided antimicrobial prescribing guidelines
3. Non-adherence with the guidelines = using a different antimicrobial agent (s) compared to that suggested in provided antimicrobial prescribing guidelines

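### Prescribing prevalence (secondary endpoint 6) is framed only as before-after, with 2019 surveys as the 'before' for paper and app; the app effect should come from the randomised app-versus-paper contrast

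*Combined protocol and SAP*

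**What the plan says.** - **Historical comparator.** Section 3.5 a (Pre-study phase) states "Antimicrobial prescription data of all six hospitals are available for the whole of 2019" and continues "These data will be used in this project to compare the change in proportion of antimicrobial prescriptions and the change in administration route". The sentence goes on to name both the paper and the app versions.
- **Endpoint 6.** Section 3.6 gives "Proportion of patients admitted to hospital receiving an antimicrobial prescription before and after introduction of the paper-based prescribing guidelines" and then adds the app with AMS training. Secondary objective 6 is worded the same way. Neither names a contrast of app against paper.
- **Endpoint 2.** For route, Section 3.6 does name that contrast: "Proportion of patients prescribed antimicrobials by the intravenous route in mobile phone app versus paper-based groups of 12 months' exposure in each group". Secondary objective 2 agrees: "To compare the change in proportion of patients receiving intravenous antimicrobials route between paper-based and mobile phone app prescribing guidelines". (The synopsis version of endpoint 2 names the oral route instead; the two need reconciling.)
- **In-trial baseline.** Section 3.5 b plans a month 0 survey in every hospital "to collect baseline data before introducing paper-based guidelines".
- **Roll-out of paper.** The start-up activities in Section 3.5 b include "Access to paper prescribing guidelines for all 6 hospitals". Section 3.4 randomises only the order in which the three hospital pairs receive the app.
- **Analysis.** The Statistical analysis section writes its logistic mixed model for adherence. It gives no model for prevalence or route, does not say how 2019 data would enter, and lists no calendar-period term.

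**The concern.** A comparison of app-phase surveys with 2019 does not use the one thing the trial randomises. By the time a hospital is surveyed on the app, several things have changed since 2019 besides the app and AMS training:

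- It has had the paper guideline for at least four months.
- It has received trial survey reports after earlier rounds.
- In three hospitals (Salavan, Xiengkhuang, Luang Namtha) another 18-month AMR programme has been running since about the start of the project (Risks section).
- The Ministry's first AMS training, planned for mid-2020 in some pilot hospitals (Introduction), may have taken place. The documents do not say whether any trial hospital is a pilot.
- Time has passed.

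For paper, any comparison with no guideline is uncontrolled by design. At stake is the interpretation of endpoint 6: a change in prevalence could be credited to the app, or to the guideline, when it has another source.

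**Working it through.** The plan states no figure for prevalence or route; its only power statement concerns adherence and does not bear on this point. The check therefore asks what each comparison would show if neither format had any effect but prevalence drifted steadily.

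**Inputs from the documents.** Each survey precedes any switch made at that visit (Section 3.5 c.3, Figure 2). From month 4 on, the hospital-surveys are:

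| Survey | Period | On paper | On app |
|---|---|---|---|
| Month 4 | 1 | 6 | 0 |
| Month 8 | 2 | 4 | 2 |
| Month 12 | 3 | 2 | 4 |
| Month 16 | 4 | 0 | 6 |

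**Assumptions.** A linear trend of b percentage points per four-month period, common to all hospitals, with b = 1, 2 or 3. The 2019 data sit g periods before month 0, with g = 1. The documents give neither b nor g.

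**Mean timing.**
- Paper: (6×1 + 4×2 + 2×3)/12 = 20/12 = 1.67 periods, or month 6.7.
- App: (2×2 + 4×3 + 6×4)/12 = 40/12 = 3.33 periods, or month 13.3.

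**Spurious change with no true effect.** Against 2019 it is b × (mean period + g). Against month 0 it is b × mean period.

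| Comparison | b = 1 | b = 2 | b = 3 |
|---|---|---|---|
| App vs 2019 (4.33b) | 4.3 | 8.7 | 13.0 |
| Paper vs 2019 (2.67b) | 2.7 | 5.3 | 8.0 |
| App vs month 0 (3.33b) | 3.3 | 6.7 | 10.0 |
| Paper vs month 0 (1.67b) | 1.7 | 3.3 | 5.0 |
| App vs paper, period and hospital effects | 0 | 0 | 0 |

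Each further period of gap before month 0 adds b to the first two rows. The last row is 0 because at months 8 and 12 app and paper hospitals are surveyed in the same round and carry the same drift, which the period effect removes. Without a period term the protection is lost: the crude pooled app-minus-paper difference is b × (3.33 − 1.67) = 1.67b, or 1.7, 3.3 and 5.0 points.

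**Would such a drift look real?** As an illustration only, take the 2018 in-patient figure ("Of 1,981 in-patient hospitals chart screened, 72% documented an antimicrobial (s) prescription") as the prevalence, with 1,981 charts on each side and clustering ignored. The standard error of the difference is √(2 × 0.72 × 0.28/1,981) = 1.43 points. A two-sided 5% test then declares a drift of 2, 3 or 5 points significant 29%, 56% or 94% of the time. With 1,000 charts a side the figures are 17%, 32% and 70%.

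**The case against.** **Route already has the right endpoint.** This stands. A reader of Section 3.5 a might infer that route is to be judged only against 2019 and that randomisation is thrown away for it. Objective 2 and endpoint 2 say otherwise. For route, the 2019 comparison is an additional and weaker analysis, not a replacement.

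**The 2019 data may well be comparable.** This also stands. One might infer that the 2019 surveys differ in kind, for example by covering in-patients only, so that adding out-patients would shift the route figures. The documents do not describe what the 2019 rounds covered. The in-patient chart count quoted above is from 2018 in five hospitals. The 2019 data come from the same six hospitals, and Appendix A4 says the survey is based on Global-PPS. In- and out-patient data are collected on separate forms (Section 3.7), and endpoint 6 concerns admitted patients, so out-patient mix cannot distort it. Unlike coverage is possible but not shown.

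**Section 3.5 a attaches no test or causal claim, and a before-after look is the only way to see what the paper guideline did.** The second half is right: app versus paper answers a different question. But the month 0 survey is a closer baseline by the trial's own method, and Section 3.5 a does not name it for these outcomes. Nor does the text call the 2019 comparison descriptive or confine it to paper.

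**Endpoint 6 ends by referring to 12 months' exposure in each group, which hints at a group comparison.** A hint is not a defined contrast, and no model for this endpoint settles the matter.

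**Conclusion.** The concern holds in a narrow form, as a cheap improvement to secondary endpoints; the primary endpoint is untouched. The main gap is endpoint 6, which is framed only as before-after although the month 4 to 16 surveys already allow the randomised app-versus-paper contrast. For endpoint 2 that contrast is planned and only needs to be given precedence over 2019.

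The size is illustrative: about 4 to 13 points of spurious app-versus-2019 change for an assumed trend of 1 to 3 points per four-month period and an assumed gap of one period. The value of 0 for the recommended contrast rests on a period term, which the written model does not list, and on a trend common to all hospitals. The AMR programme runs in both northern hospitals and one southern hospital, so its effect need not be common. The randomised contrast is much less exposed to it than a comparison with 2019, but not immune.

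**What to change.** 1. In objective 6, endpoint 6 and the Statistical analysis section, define the app effect on prevalence as app plus AMS training against paper, estimated from the month 4, 8, 12 and 16 surveys in a logistic mixed model with a fixed effect for each survey round and a hospital effect. State that endpoint 2 uses the same model and that this contrast takes precedence.
2. Name the month 0 survey as the main pre-guideline baseline for any before-after description of paper. Reconcile Section 3.3, which places the baseline measurement after paper is introduced, and the Statistical analysis section, which counts month 0 in the reference arm, with Section 3.5 b.
3. In Section 3.5 a, label the 2019 comparison descriptive and do not use it for the app effect. Report in- and out-patients separately, limited to settings and calendar months that the 2019 surveys share with the trial surveys, and state what those surveys covered.

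The cost is wording in the protocol and SAP, with no new data. The downside is that the paper guideline's own effect gets no formal test, which the design does not support in any case. The plan states no precision for endpoint 6, and with six hospitals randomised as three pairs the interval may be wide.

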Each participating hospital will participate this survey only once before they enter to the intervention period. The aim of the survey is to get feedback on the provided paper-based prescribing guidelines from the prescribers as well as self-reported use of the guidelines. Survey form (Appendix A10. *Prescriber feedback survey on paper-based prescribing guidelines*) will include questionnaires on the frequency of the use of paper-based guidelines and Likert scale questionnaires on prescribers' opinions on the paper-based prescribing guidelines. The survey forms will be distributed to all prescribers after PPS and before introduction of the mobile phone app prescribing guidelines. By doing this, we will obtain different opinions about the paper prescribing guidelines at different time points. This will also provide feedback on the guidelines and the change in prescribing behaviours in participating hospitals exposed to paper and app

prescribing guidelines for the same duration. Complete survey forms will be collected from all prescribers at each study hospital in the same days as the survey day.

Prescriber feedback survey on mobile phone App prescribing guidelines

This survey will be conducted at the end of the study (month 16) when all participating hospitals having access to the mobile phone app at least for 4 months. The aim of the survey is to get feedback on the mobile phone app prescribing guidelines from prescribers, as well as how prescribers find this app compared to the paper version of the prescribing guidelines. The survey forms include questionnaires on the frequency of the use of paper-based guidelines after introducing mobile phone app guidelines, as well as the frequency of the use of the mobile phone app guidelines use and Likert scale questionnaires on prescribers' opinions of the mobile phone app prescribing guidelines. Complete survey forms will be collected from all prescribers at each study hospital on the same days as the survey day. The same survey form will be used for all participating hospitals (Appendix A11. *Prescriber feedback survey on mobile phone app prescribing guidelines*).

Data management and monitoring

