Training evaluation: All participating hospitals will join AMS knowledge survey three times during the study period (1st time= at the start of the project, 2nd time= before entering to the intervention period and 3rd time= at the end of the project)

A13. Antimicrobial stewardship (AMS) training session registration sheet

Antimicrobial Stewardship (AMS) Training Session Registration Form

Date: _____, Time: _____
Venue: _____, Hospital: _____

No.	Name and Surname	Age	Sex	position	Department	Years of work (year)	Phone number
1							
2							
3							
4							
5							
6							
7							
8							
9							
10							
11							
12							
13							
14							
15							
16							
17							
18							
19							
20							
21							
22							
23							
24							
25							
26							
27							
28							
29							
30							

Official DPhil start date: 29 April 2019; Transfer deadline date from PRS to DPhil is 24 April 2020; Complete confirmation DPhil status by the end of 9th term on 14th Jan 2022 (final term); Maximum submission date is 13 Jan 2023

* Prescriber feedback survey on the App will be performed in a paired hospitals/time only

	End of grant
	Maximum submission date
	Complete confirmation DPhil status

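### The app feedback survey has two incompatible schedules, and neither gives the four months of exposure to each format that secondary endpoint 4 specifies

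*Combined protocol and SAP*

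**What the plan says.** All references are to the combined protocol and SAP. Pairs are numbered in order of crossover.

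- **App survey (A11), month 16.** Section 3.5 c.3, Note a, says that it "will be performed at the end of the project only when all participating hospitals have access to the mobile phone app", and gives month 16. Note b also places it at the end of the study. Section 3.7, in the paragraph on the app feedback survey, repeats month 16, by which time every hospital has had the app for four months or more.
- **App survey (A11), pair by pair.** Figure 2 lists the survey at months 8, 12 and 16, with the footnote "This activity will only be performed 4 months after introducing App guideline in each paired hospital". The footnote to the timeline appendix agrees: "Prescriber feedback survey on the App will be performed in a paired hospitals/time only".
- **Paper survey (A10).** Paper guidelines reach all six hospitals at month 0. Section 3.5 b puts the A10 survey "just before each paired hospital enters to the intervention phase (month 4, month 8 and month 12" after that introduction). Section 3.7 says that each hospital takes it once.
- **Endpoint.** Section 3.6, secondary endpoint 4, is "Prescriber satisfaction/acceptability of the prescribing guidelines in mobile phone app versus paper-based groups", with exposure set at four months in each group. The synopsis gives the same figure. Section 3.7 adds that the hospitals rate paper and app after equal lengths of exposure.
- **Analysis.** The Statistical analysis section plans a Mann-Whitney test between the paper population and the app population, and states no exposure or pair term for it.

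**The concern.** Note a and the Figure 2 footnote each restrict the survey to their own timing, so both cannot be followed in pairs 1 and 2, which are four of the six hospitals. In pair 3 the two rules coincide at month 16.

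The paper survey is tied to crossover, so its exposure time lengthens from pair to pair whichever A11 rule is used. If opinion of a tool changes with familiarity, part of any difference between app and paper ratings could reflect time in use and not format. Exposure may also affect who rates: A10 and A11 both let a respondent stop if the guideline has never been used. A reader of the results would take endpoint 4 to compare formats at four months each, and the schedule does not provide that.

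**Working it through.** **Inputs.** Paper introduced at month 0 (section 3.5 a and b). App introduced at months 4, 8 and 12 for pairs 1, 2 and 3 (section 3.5; Appendix A7). A10 at months 4, 8 and 12 (section 3.5 b). A11 at month 16 (text) or at months 8, 12 and 16 (Figure 2).

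**Formula.** Exposure at survey = survey month − introduction month.

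| | Pair 1 | Pair 2 | Pair 3 | Mean of pairs |
|---|---|---|---|---|
| Paper (A10) | 4 − 0 = 4 | 8 − 0 = 8 | 12 − 0 = 12 | 24/3 = 8 |
| App, text | 16 − 4 = 12 | 16 − 8 = 8 | 16 − 12 = 4 | 24/3 = 8 |
| App, Figure 2 | 8 − 4 = 4 | 12 − 8 = 4 | 16 − 12 = 4 | 12/3 = 4 |
| App − paper, text | +8 | 0 | −8 | 0 |
| App − paper, Figure 2 | 0 | −4 | −8 | −4 |

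**The plan's own figure.** Four months in each group is not reproduced under either schedule.

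- *Text:* the paper/app values are 4/12, 8/8 and 12/4. No pair has four months in both formats. Only pair 2 has equal durations.
- *Figure 2:* the values are 4/4, 8/4 and 12/4. The app side does meet four months everywhere; the paper side meets it only in pair 1, which is also the only pair with equal durations.

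**Weighting by number of prescribers.** The means above count each pair equally, whereas a pooled test counts respondents. As an illustration, assume that every physician listed in section 3.2 responds: north 18 + 66 = 84, centre 222 + 30 = 252, south 60 + 30 = 90, total 426. The crossover order is set by the draw.

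- Order north, south, centre: paper (84×4 + 90×8 + 252×12)/426 = 4080/426 = 9.6 months; app under the text 16 − 9.6 = 6.4.
- Order centre, south, north: paper (252×4 + 90×8 + 84×12)/426 = 2736/426 = 6.4 months; app under the text 9.6.
- The other four orders lie between these. With the centre second, the two arms are within about 0.2 months of each other (8.1 versus 7.9, or the reverse).
- Under Figure 2 the app mean is 4.0 in every order, so it falls short of paper by 2.4 to 5.6 months.

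**The case against.** **Four months could be a minimum.** The synopsis speaks of ratings after four months' exposure, and section 3.7 describes month 16 as giving at least four months of app access. Both schedules satisfy a minimum. But section 3.6 gives four months as the exposure in each group and does not call it a floor. This is an ambiguity to remove, not an answer to the point.

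**Under the text, the arms are balanced overall.** The test is unpaired and the forms are anonymous. Paper exposures are 4, 8 and 12 months and app exposures are 12, 8 and 4, so by pair the two arms hold the same set of durations. At arm level the equal-duration sentence in section 3.7 can be read as met. This largely stands, subject to hospital size, but neither arm is then at four months.

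**The staggered paper survey is deliberate.** Section 3.7 wants views of the paper guidelines after differing lengths of use. That explains the A10 timing and should be respected. It does not reconcile that timing with endpoint 4.

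**Equal exposure would not make the ratings fully comparable.** A10 has 17 rating items and A11 has 10, with few in common. That is true, but it is a separate limitation.

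**Stronger readings that the documents do not support.** A reader might infer that the mismatch runs in opposite directions across pairs whichever rule is used. That is so only under the text (+8, 0, −8); under Figure 2 (0, −4, −8) it is never in the app's favour. A reader might also infer that the text schedule systematically favours one format, but the equal pair means do not show that. Nor do the documents say which schedule was intended: Figure 2 and the timeline footnote stand against Notes a and b and section 3.7.

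**Conclusion.** The inconsistency is real and should be corrected. Two incompatible A11 schedules stand in current text, and with A10 fixed at crossover neither delivers four months' exposure in each group. Under the text, none of the three pairs meets it, although the pair means are equal at 8 months. Under Figure 2, one of three meets it, and the imbalance is always towards less app exposure (means 8 versus 4).

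This rests on reading each group as the app or paper arm, and four months as the exposure and not a minimum; section 3.6 favours both readings. The size of any resulting bias in ratings cannot be derived from the documents, because they do not say how ratings change with time in use. The issue is confined to secondary endpoint 4. The primary endpoint and the power statement are untouched, and nothing here suggests otherwise.

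**What to change.** First, choose one A11 schedule and make Notes a and b, the section 3.7 paragraph, Figure 2 and the timeline footnote agree. Then take one of two routes.

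1. **Meet the endpoint as written.** Keep A11 at four months after introduction in each pair, and give A10 at month 4 in all six hospitals. Compare the four-month ratings. Keep the pre-crossover A10 in pairs 2 and 3 as additional data, which preserves the aim of collecting views after differing lengths of use. The cost is one extra short survey round in four hospitals. A prevalence survey takes place in every hospital at month 4, but section 3.7 allows a trained local doctor to run it, so the study team's presence should not be assumed. State also whether the end-of-study check on use of both formats in Note b is kept.
2. **Restate the endpoint.** Keep the existing A10 timing. Rewrite endpoint 4 (synopsis and section 3.6) and the equal-duration sentence with the actual exposures, which range from 4 to 12 months. Report the app-versus-paper comparison by pair or by exposure duration. The cost is wording and a small addition to the analysis plan; the comparison is then no longer one at a common four months.
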